10.3 Procedure for Breaking the Randomisation Code

Emergency treatment code breaks should only be undertaken when it is essential to treat the subject safely and efficaciously. Most often, investigational treatment discontinuation and knowledge of the possible treatment assignments are sufficient to treat a study subject who presents with an emergency condition. Emergency code breaks are performed using the IRT. When the investigator contacts the system to break a treatment code for a subject, he/she must provide the requested subject identifying information and confirm the necessity to break the treatment code for the subject. The investigator will then receive details of the investigational drug treatment for the specified subject and a fax or email confirming this information. The system will automatically inform the ICON site monitor, the medical monitor, and the ICON Project Manager that the code has been broken, but no treatment assignment will be communicated.

It is the investigator's responsibility to ensure that there is a procedure in place to allow access to the IRT in case of emergency. The investigator will inform the subject how to contact his/her backup in cases of emergency when he/she is unavailable. The investigator will provide the protocol number, investigational treatment name if available, subject number, and instructions for contacting the local entity which has responsibility for emergency code breaks to the subject in case an emergency treatment code break is required at a time when the investigator and backup are unavailable.

10.4 Subject Compliance

Each time study medication is dispensed subjects will be informed about compliance. When study medication is returned, compliance will be assessed based on the subject's interview and a count of the tablets. The investigator (or designee) will record the amount of study medication dispensed and returned at each visit, as well as document the reasons for non-compliance in the source document. The investigator will record the date and time of the study drug intake to the EDC. The subject should be re-educated regarding treatment compliance and/or recording dose. A significant noncompliance with protocol or study drug will be communicated to the sponsor.

10.5 Study Treatment Accountability

Records shall be maintained of the delivery of study treatments to the study centres, the inventory at the study centres, the use of each subject and the return to the sponsor.

These records shall include dates, quantities, batch numbers, expiry dates and the unique code numbers assigned to the study medication and to the study subjects.

The investigator shall be responsible for ensuring that the records adequately document that the subjects were provided the doses specified in the protocol and that all study medication

received from the sponsor is reconciled. All study medication must be returned to the sponsor at the end of the study.

10.6 Contraception

Semen samples will be collected after a minimum of 48 hours of sexual abstinence, therefore no sexual activity should be performed in this time period and no spermicidal cream used to avoid interference with semen evaluation.

10.7 Prohibited Therapy

The following classes of medication listed below are not permitted to be taken during the conduct of the study starting from Screening (for details of Screening criteria concerning medications, see [Section 9.3.1](#) and [Section 9.3.2](#)):

1. Over the counter or ordered via the internet or prescribed medications that are known to influence production or efficacy of sex hormones, or with oestrogen/androgen-like or antioestrogen/antiandrogen-like properties e.g.,
 - Opiates/Opioids including methadone for > 7 consecutive days during study duration
 - Chronic systemic steroid treatment or systemic steroids for > 5 consecutive days for intercurrent illness (inhaled and topical steroids are allowed)
 - Medications known to increase prolactin levels, e.g., antipsychotics
 - 5- α -reductase inhibitors, e.g., Finasteride
 - Spironolactone
 - Cimetidine
 - Growth hormone
 - Testosterone, known testosterone enhancers, anabolic steroids, known active Fertility drugs and Oestrogens or selective oestrogen receptor modulators (SERMS)

- Clomid
- Bisphosphonates, Teriparatide, Denosumab (treatment with calcium and vitamin D for bone health is allowed at the discretion of the investigator)

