9.3.2 Exclusion Criteria

1. Evidence of clinically significant endocrinopathy at Screening that may interfere with the study assessments or mask/mimic symptoms of hypogonadism e.g., growth hormone deficiency, adrenal deficiency, untreated hypothyroidism (primary hypothyroidism on

- replacement with normal thyroid stimulating hormone [TSH] level is allowed), or that may interfere with the evaluation of efficacy/safety parameters
2. Other types of HH (e.g., Kallmann syndrome) or primary hypogonadism (e.g., cryptorchidism, or Klinefelter syndrome)
 3. Any other pituitary or hypothalamic disease, as based on one of the following:
 - Current or past hypothalamic or pituitary tumour
 - Suspicion of pituitary or hypothalamic tumour based on a clinical or laboratory evidence, e.g., elevated prolactin or other pituitary hormone abnormality, symptoms/signs of tumour mass effect, very low testosterone and LH (unless there is documentation of a normal magnetic resonance imaging scan of pituitary and hypothalamus within 3 months before first Screening Visit)
 - Hypothalamic or pituitary conditions, which may contribute to hypogonadism e.g., pituitary sarcoidosis, histiocytosis or tuberculosis
 4. Subject with prostate disease, as confirmed by the presence of one of the following:
 - History of prostate cancer
 - Elevated PSA levels ≥ 3 ng/mL at Screening
 - Subjects with a detectable prostate nodule or induration at Screening unless proven previously benign by a biopsy
 - Urologist confirmed symptomatic benign prostatic hyperplasia
 5. History of type 1 diabetes mellitus
 6. Current clinically symptomatic depression or current or past Bipolar disorder
 7. Uncontrolled type 2 diabetes mellitus (HbA1c $> 10.5\%$ at Screening) or significant diabetic neuropathy. Subjects with type 2 diabetes can be included when both of the following conditions are met:
 - HbA1c $\leq 10.5\%$ at Screening, and:
 - Anti-diabetic medication regimen has been stable for ≥ 8 weeks before the first Screening visit
 8. Treatment with one or more of the following prescribed or over the counter medications in the six months prior to first Screening Visit:
 - Medications with known androgenic or estrogenic properties or known to affect production of sex hormones
 - Injectable testosterone enhancement therapy
 - Fertility drugs
 - Growth hormone
 - Anabolic steroids
 - Long acting opiates

9. Treatment with topical testosterone therapy in the two months prior to first Screening visit

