5 SAMPLE SIZE AND POWER

The sample size for this study is calculated using exact binomial methods for comparison of a single proportion to a performance goal.

The statistical hypothesis is the proportion of subjects that have normalisation of testosterone at Week 24 within a dose group is greater than the pre-specified performance goal of 75%:

H0: Normalisation \leq 75%

H1: Normalisation $>$ 75%

The calculation assumes a one-sided test conducted at the 2.5% significance level, for which 67 subjects will need to be randomised in each dose group of BGS649.

If the true normalisation rate in a dose group of BGS649 is 90% then the power of the study is 85%.

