8.6.4.3 Changes in Cardiometabolic Disease Markers

Descriptive summary tables will be presented for blood pressure (systolic and diastolic blood pressure), fasting lipid profile (total cholesterol, low density lipoprotein [LDL], triglycerides and HDL), HbA1c, fasting glucose, fasting insulin, high sensitivity C reactive protein (hs CRP) and HOMA-IR values and change from baseline values by treatment regimen and visit.

The change from baseline in each parameter up to Week 24 will be analysed via MMRM in the same manner as the change from baseline in total testosterone (see Section 8.6.3.1).

Non-fasting values of all lipid profile parameters, glucose and insulin will be excluded from both the descriptive summary and analysis.

In addition the number and proportion of subjects who met the definition of metabolic syndrome will be summarised by treatment regimen at each visit (baseline and post-baseline).

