8.6.4.5 Change in PRO measures

For some PRO Measures (PROMIS SexFS, PROMIS Fatigue Short Form and PGI-S), not all protocol versions mandated their collection. Subjects originally enrolled using protocol versions 2.0 were not required to collect these measures. To handle such cases, denominators used for analysis will only include the subjects mandated to collect the particular PRO.

IIEF

Descriptive summary tables will be presented for each of the 5 sexual function domain scores (Erectile function, Orgasmic function, Sexual desire, Intercourse satisfaction and Overall satisfaction) and change from baseline scores by treatment regimen and visit.

The change from baseline in each sexual function domain score to Week 24 will be analysed via MMRM in the same manner as the change from baseline in total testosterone (see Section 8.6.3.1), however 90% confidence intervals (instead of 95%) will be presented for all inferences.

The number and proportion of subjects achieving a minimal meaningful difference in the change in IIEF erectile function domain score will be summarised by treatment regimen at each visit and overall.

In addition the change from baseline in the IIEF domains will also be summarised and analysed as described above by erectile function baseline severity (No dysfunction, mild, moderate and severe), baseline total testosterone (<200ng/dL vs \geq 200ng/dL) as assessed by ICON central labs and end of treatment total testosterone (<300ng/dL, 300-500 ng/dL and >500ng/dL) as assessed by ICON central labs.

PROMIS SexFS

Descriptive summary tables will be presented for each of the 3 sexual function domains scores (Interest in Sexual Activity, Erectile Function, Satisfaction with Sex Life), 2 interfering factors raw

scores and change from baseline scores (domain and interfering factor raw scores) by treatment regimen and visit.

The change from baseline in each sexual function domain score and 2 interfering factor raw scores to Week 24 will be analysed via MMRM in the same manner as the change from baseline in IIEF domain scores including subgroup analysis by baseline total testosterone (<200ng/dL vs \geq 200ng/dL) and end of treatment total testosterone (<300ng/dL, 300-500 ng/dL and >500ng/dL) as assessed by ICON central labs.

PROMIS Fatigue Short Form

A descriptive summary table will be presented for the PROMIS Fatigue Short Form standardised T-Score and change from baseline score by treatment regimen and visit.

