8.7.3 Vital signs

Vital sign assessments will be performed at each visit in the Randomisation Phase and Week 36.

Descriptive statistics (observed values and changes from baseline) will be presented for each treatment regimen and time-point for vital sign measurements (body temperature, pulse rate, systolic blood pressure, diastolic blood pressure, weight and BMI).

The change from baseline in systolic and diastolic blood pressure to Week 24 will also be analysed via MMRM in the same manner as the change from baseline in total testosterone (see Section 8.6.3.1).

Boxplots of observed and change from baseline values by treatment and visit will also be generated for both systolic and diastolic blood pressure.

In addition the number and percentage of subjects meeting each of the criteria below will be presented:

- Normal: SBP <120mm Hg and DBP < 80 mm Hg
- Elevated BP: 120≤SBP ≤ 129 mm Hg and DBP < 80 mmHg
- Hypertension Stage 1: 130≤SBP ≤ 139 mmHg or 80≤DBP ≤ 89 mmHg
- Hypertension Stage 2: SBP ≥ 140 mm Hg or DBP ≥ 90 mmHg

- SBP Change from baseline ≥20 mmHg
- DBP Change from baseline ≥10 mmHg

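### The SAP has no rule for erectile-dysfunction, blood-pressure, glucose or lipid drugs started or increased during treatment, so IIEF, blood-pressure and metabolic comparisons can be biased in either direction

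*Protocol*

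**What the plan says.** **Drug restrictions.** Protocol 10.7 begins "The following classes of medication listed below are not permitted to be taken during the conduct of the study starting from Screening". Its list covers drugs acting on sex hormones (including opioids, systemic steroids, prolactin-raising drugs, spironolactone and cimetidine), growth hormone and bone drugs. Spironolactone is the only listed drug that also lowers blood pressure. No erectile-dysfunction, glucose-lowering or lipid-lowering class appears.

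**Entry rules look backwards.** Protocol 9.3.2, criterion 7, admits type 2 diabetes with HbA1c up to 10.5% if "Anti-diabetic medication regimen has been stable for" at least 8 weeks before the first Screening visit. The synopsis version leaves insulin out of that stability condition; the two versions should be reconciled. Criterion 19 excludes uncontrolled hypertension in the 3 months before Screening. Neither criterion governs the 24 treatment weeks.

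**Analysis.** The MMRM in SAP 8.6.1 contains treatment, visit, baseline and their interactions with visit, and no medication term.
- SAP 8.6.4.5 models the IIEF domains and reports "The number and proportion of subjects achieving a minimal meaningful difference in the change in IIEF erectile function domain score".
- SAP 8.7.3 states "The change from baseline in systolic and diastolic blood pressure to Week 24 will also be analysed via MMRM".
- SAP 8.6.4.3 has one value-level exclusion: "Non-fasting values of all lipid profile parameters, glucose and insulin will be excluded from both the descriptive summary and analysis".
- SAP 8.4.4 tabulates concomitant medication by ATC level 4. Under SAP 7.1.4.3 a drug already in use on Day 1 and one started in Week 10 are both concomitant.

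**Insulin.** Protocol 11.3.3 says insulin use is recorded so that the insulin and HOMA-IR analyses can remove its effect. The SAP has no such step, and SAP section 9 lists only the vitamin D cut-off as a change from the protocol.

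**The concern.** A man who starts an erectile-dysfunction drug and then reaches the IIEF threshold is counted as a responder to his randomised treatment. A man whose blood pressure rises and is treated contributes the treated value to later visits of the MMRM. HbA1c after intensified diabetes therapy is attributed to the study arm. If such starts differ between arms, the contrast mixes the effect of BGS649 with the effect of the added drugs.

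Blood pressure matters most, because the SAP gives it a model, boxplots, hypertension categories, change thresholds and association plots. The IIEF also matters: every man needed at least one sexual-dysfunction symptom at entry, so sexual function bears on whether a testosterone response is felt as a benefit. In SAP 8.8.4.2 the same responder variable is regressed on testosterone category, so drug starts that differ by testosterone level would distort that association too.

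**Working it through.** **1. The plan's own figure.** SAP section 5 sizes the trial for testosterone normalisation: 67 per dose group, goal 75%, true rate 90%, power 85%. "The calculation assumes a one-sided test conducted at the 2.5% significance level". Exact binomial: success needs at least 58 of 67, attained alpha 0.016, power 87.1%. The continuity-corrected normal approximation gives n = 66.3, rounded up to 67, with power 85.5% at 67. The figure reproduces with the latter method, and only the 67 is carried forward. The documents give no effect size, SD or power for IIEF, blood pressure or metabolic markers, and no usage rates. Everything below is assumed.

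**2. IIEF responders.** Assume 50% (active) and 25% (placebo) respond without added drug, a share s of each arm starts an erectile-dysfunction drug, and 90% of starters then reach the threshold.
- Model A, starters are any men: observed rate = (1 − s)p + 0.9s.
- Model B, only men who would not have responded start: observed rate = p + 0.9s.

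Power is for a two-sided 5% Fisher test (the binary-outcome method in SAP 8.6.1), by exact enumeration at 67 per arm.

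| Start rate, active / placebo | Model A: rates, difference, power | Model B: rates, difference, power |
|---|---|---|
| 0% / 0% | 50.0 vs 25.0, 25.0 points, 81% | same |
| 4% / 10% | 51.6 vs 31.5, 20.1 points, 59% | 53.6 vs 34.0, 19.6 points, 55% |
| 8% / 8% | 53.2 vs 30.2, 23.0 points, 71% | 57.2 vs 32.2, 25.0 points, 78% |
| 10% / 4% | 54.0 vs 27.6, 26.4 points, 84% | 59.0 vs 28.6, 30.4 points, 93% |

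More use on placebo dilutes the difference and more use on active inflates it. Equal use dilutes under A and leaves the difference unchanged under B. The 67 is an upper limit: SAP 7.1.3.3 defines the minimal meaningful difference only for men with mild, moderate or severe dysfunction at baseline.

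**3. IIEF erectile-function mean.** Observed difference = true difference − (placebo use − active use) × drug gain. With a true 5 points and a gain of 4 to 8 points:
- 10% in both arms: 5.0
- placebo 20%, active 5%: 4.4 to 3.8
- placebo 30%, active 10%: 4.2 to 3.4
- placebo 5%, active 15%: 5.4 to 5.8

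**4. Systolic blood pressure.** Observed rise = true rise − (active use − placebo use) × drug fall. With a true 5 mmHg and a fall of 5 to 15 mmHg:
- equal use: 5.0
- active 20%, placebo 5%: 4.25 to 2.75
- active 30%, placebo 5%: 3.75 to 1.25

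More starts on placebo would exaggerate the rise: with active 5%, placebo 20% and a fall of 10, 5 + 0.15 × 10 = 6.5 mmHg.

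**5. HbA1c.** With a true −0.2 percentage points and a step-up worth −1.0, placebo 10% versus active 5% gives −0.2 + 0.05 × 1.0 = −0.15. Reversing the rates gives −0.25.

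**The case against.** **The direction is not known.** A reader might infer that IIEF effects are necessarily diluted, because men who do not improve seek extra treatment. The working does not support that: the bias can be zero or reversed, and the documents give no rates. This objection stands. It limits what can be claimed about direction, but does not close the gap.

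**Blood-pressure safeguards exist.** A reader might infer that a rise would go unseen. Protocol 12.1.4 makes a vital-sign abnormality reportable when it is clinically significant or needs further testing or intervention, and SAP 8.7.1 tabulates treatment-emergent events by preferred term and regimen. SAP 8.7.3 also counts rises of at least 20 mmHg systolic or 10 mmHg diastolic, so a rise recorded at a scheduled visit before treatment still counts. This stands. What remains is the MMRM mean at later visits, and a rise found and treated between scheduled visits, since SAP 8.1.7 lists unscheduled results without tabulating them.

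**Using all values can be legitimate.** It matches a treatment-policy approach, so it cannot be said that the SAP treats these men as untreated; it is silent. Dropping post-start scores in the main IIEF model would be a change of estimand resting on a missing-at-random assumption. The all-scores model should therefore stay as the planned analysis.

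**Two further readings fail.** A man does not become an IIEF responder merely by starting a drug; he must reach the threshold in SAP 7.1.3.3. Nor was erectile dysfunction required at entry: inclusion criterion 6 asks for a sexual dysfunction, and Appendix II also lists reduced desire and reduced orgasm intensity.

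**The stakes are limited.** The IIEF and metabolic endpoints are exploratory, and Protocol 13.5.1 describes all analyses as exploratory.

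**Conclusion.** The gap is real and specific. These drug classes may be started or increased during treatment (spironolactone apart), and the SAP does not say what happens to later values. The per-protocol set does not help, because use of a permitted drug is not a violation. SAP 8.8.3 covers only baseline covariates for the primary endpoint.

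On the assumed rates the IIEF responder difference lies between about 20 and 30 points, against 25 with no starters, and power between about 55% and 93%, against 81%. An assumed 5 mmHg systolic rise could read as low as 1.25 mmHg if antihypertensives are started much more often on active. These ranges show sensitivity and are not predictions. Neither certain dilution nor a hidden blood-pressure signal follows from the documents, and the primary testosterone endpoint is untouched.

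The protocol already accepts the principle for exogenous insulin, and the SAP does not carry it out. Because the direction is unknown, the rule should be fixed before anyone sees use by arm.

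**What to change.** Change the SAP only, using the concomitant medication already recorded at treatment visits and classified blind at the Classification Meeting.

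1. **SAP 8.6.4.5 and 8.8.4.2.** Count a man who starts or increases an erectile-dysfunction drug after Day 1 as a minimal-meaningful-difference non-responder from that date. Keep the all-scores IIEF and SexFS MMRMs as planned and add a supplementary run without scores after the start.
2. **SAP 8.7.3.** Add one row per regimen for men with a systolic rise of at least 20 mmHg, or a diastolic rise of at least 10 mmHg, or a started or increased antihypertensive. Add a supplementary blood-pressure MMRM without values after the start.
3. **SAP 8.6.4.3.** Add supplementary HbA1c, glucose and lipid MMRMs without values after a started or increased drug of the relevant class. Write in the exogenous-insulin exclusion for insulin and HOMA-IR intended by Protocol 11.3.3.

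Cost: SAP wording, blinded coding of a few drug classes and some extra model runs. The supplementary runs rest on a missing-at-random assumption. The non-responder rule redefines response as response without an added drug. Under Model B it returns exactly 25 points at every start rate shown. Under Model A the rates become p(1 − s), giving 48.0 − 22.5 = 25.5, 46.0 − 23.0 = 23.0 and 45.0 − 24.0 = 21.0 points, so it counts against the arm with more starters. The documents do not say whether dose is captured; if it is not, the rules can cover only starts. Protocol 10.7 and clinical management stay as they are.

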11 ASSESSMENT OF EFFICACY

11.1 Efficacy and Pharmacokinetic Variables

1. Total and bioavailable testosterone, LH, FSH, inhibins (A and B), oestradiol (total)
2. Testosterone/oestradiol ratio
3. Body composition:
 - Body weight and BMI
 - Waist circumference, hip circumference and waist to hip ratio
 - Gynecomastia
 - Fat and muscle percentage (by impedance)
4. Cardiometabolic parameters
 - Blood pressure (DBP and SBP)
 - Fasting lipid panel (total cholesterol, LDL, HDL, triglycerides)
 - HbA1c
 - Fasting glucose and insulin
 - hs-CRP
 - HOMA-IR (see [Section 11.3.3](#) for details)
5. PRO measures
 - International Index of Erectile Function (IIEF) and PROMIS Sexual Function and Satisfaction (PROMIS SexFS): to assess improvement in erectile function.
 - IIEF and PROMIS SexFS: to assess improvement in sexual desire and satisfaction with sex life.
 - 36-item Short Form Health Survey (SF-36): to assess general quality of life (QoL) .
 - Brief Fatigue Inventory (BFI), PROMIS Fatigue Short Form and the SF-36 Vitality: to assess improvement in energy levels.
 - Patient Global Impression of Status items (PGI-S): to assess the patients' overall impression of their current health status.
6. Actigraphy derived activity and sleep parameters
 - Counts of sedentary, moderate and vigorous activity
 - Sleep quality and duration
7. Dynamometry derived grip strength assessment
8. Semen analysis
 - Sperm count
 - Sperm concentration
 - Volume of semen

- Sperm motility
 - Sperm morphology
9. PK plasma analysis and PK semen analysis.

Detail of assessment of the efficacy and PK variables are presented in [Section 11.3](#) and [Section 11.4](#), respectively.

